### **Follow-Up**

Patients will be asked to wear and sync the device they received, Apple Watch Series 6 or Withings Move, from the time of enrollment forward for 12 months. This includes wearing it at all outpatient visits and opening the Withings Health Mate or Hugo Health iPhone applications every 7 days to ensure data syncs. We will ask patients to obtain an Apple Watch ECG whenever they obtain an ECG in routine clinical care, and to record symptoms that they had at the time of obtaining the ECG. They will be asked not to share the Apple Watch with anyone else for the 12-month duration of the study, nor their iPhone or iCloud accounts. We will suggest people charge their Apple Watch for the minimum necessary time and try to wear it for as much time as possible. We will not provide any anticipatory guidance to people about what they are supposed to do if they receive an irregular rhythm notification or a reading on their ECG app reading showing atrial fibrillation, as the goal of the study is to observe the natural history of patient-reported outcomes and health care utilization in response to device use.

Based on experience from prior studies, we anticipate being able to successfully and seamlessly stream electronic health record as well as patient-generated data from the Apple Watch and Apple HealthKit (including irregular rhythm notifications, high heart rates, low heart rates, and other data, which may include SpO2), as well as from the Health Mate platform for patients randomized to Withings Move, into our researcher database using the Hugo platform. For the AFEQT questionnaire, patients will receive this via secure email or text message link monthly for 6 months and then at 12 months. During the first 6 months, if they do not respond within 24 hours, they will receive a reminder. If they do not respond within 48 hours, they will receive a second reminder. Should there still be no response after an additional 48 hours, the RA will reach out to the patient via phone to follow-up to ask the patient to complete the unanswered survey.

A weekly automated reminder (text or email – based on the patient’s preference) will be sent from Hugo, reminding patients to wear and sync their device. If no data are received, the RA will reach out to the patient via phone to follow-up. RAs will record if they successfully reach patients and if reasons for lack of data are identified.

Additionally, patients in the control (Withings Move) arm will receive a small stipend in addition to the Withings Move for completion of PROMs (patients in the Apple Watch arm will have received an Apple Watch, which we will explain comes with the expectation of responses to monthly PROMs, which would not be expected to take more than 5-10 minutes). We will also ask patients to obtain a final Apple Watch ECG at 6 months. Patients will be asked to share all of their Apple Watch-obtained ECGs with the research team by sending them to [contact]. which has been created specifically for this study. For patients randomized to the Apple Watch, we will also send them a reminder at the end of the 6 months to send us any ECGs that they may have obtained on their device. We will also attempt to obtain ECGs directly through a connection between Hugo and Apple.

If patients choose to share other data, such as by connecting their pharmacies or claims, through the Hugo platform that will be noted in our study and those data will be made available for analyses.

If a patient reaches out to any member of the study team to withdraw from this study, we will ask if he/she would be willing to share why they have decided to withdraw. If they are willing to share, we will document that reason.

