
12. **Statistical Considerations:** Describe the statistical analyses that support the study design.

All analyses will be intention-to-treat. For the primary outcome, we will calculate the difference in the AFEQT global questionnaire score at baseline and 6 months for patients randomized to the Apple Watch and patients randomized to the Withings Move arm.

The secondary clinical utilization outcomes will also be compared between the two groups using an intent-to-treat approach. Hugo will be the primary mechanism used to obtain clinical outcomes and clinical utilization, with comparisons between groups. We will also trend patients' monthly responses about anticoagulation adherence. In an additional secondary analysis, we will examine all of the outcomes at 12 months.

For the secondary outcomes for accuracy of Apple Watch Software Features that will be compared are a comparison of the heart rhythm (identical to 12-lead ECG or different), rate (difference in beats per minute), and PR, QRS, and QT intervals (difference in milliseconds) between what is assessed by the Apple Watch ECG feature and 12-lead ECGs during hospitalization or outpatient follow-up care. We will aim to compare the SpO2 readings taken by the Apple Watch at baseline to the measure taken by the standard, medical grade pulse oximeter

This sample size was calculated assuming 80% power to detect an effect size of 8.8 on the AFEQT questionnaire (slightly higher than the minimal clinically important difference of 5), with alpha 0.05.

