### 1.4 SAMPLING PROCEDURE, SAMPLE SIZE AND POWER CALCULATION

The study sample size was calculated assuming 80% power to detect an effect size of 8.8 on the AFEQT questionnaire (slightly higher than the minimal clinically important difference of 5), with alpha 0.05.

We expect that drop-out rate will be close to zero in this study as patients are followed passively and the burden on patient is minimal. In terms of non-completion of the 6-month AFEQT Questionnaire, our

current study accounts for an estimated drop-out rate of 8% at 6 months based on the use of the AFEQT score from Holmes DN et al Circ Cardiovasc Qual Outcomes 2019, in which the mean  $\pm$  SD was  $79.0 \pm 18.5$  and assuming an effect size of 8.8 on the AFEQT questionnaire, which is higher than the minimal clinically important difference of 5.

If patient drop-out or loss to follow-up occurs, then we will carry forward the last patient-reported outcome measure response. If an electronic health record data connection is lost for a study participant, we will only include the follow-up duration when data were available in the utilization endpoint analyses.

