## 1.6 ENDPOINT ANALYSIS

### 1.6.1 PRIMARY ENDPOINT ANALYSIS

For the primary outcome, we will calculate the difference in the AFEQT global questionnaire score (as this is a continuous variable) at baseline and at 6 months and perform a comparison between the patients randomized to the Apple Watch and patients randomized to Withings Move. This will be calculated as per standard AFEQT calculations, which result in a summary score for this continuous outcome (which ranges from 0 to 100). We will use a t-test for this comparison. As this is an RCT, we expect that confounding will be minimal. If patients are missing outcome data, we will use the last observation carried forward for the patient-reported outcomes. Missing covariates will be set to missing.

At 12 months, we will also perform the same analysis, but this will be as an exploratory secondary endpoint. If a patient drops out, we will carry forward the most recent patient-reported outcome measure response.

We will also retrospectively compare AFEQT global questionnaire at months 1, 2, 3, 4, 5.

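### No reminder or phone follow-up is specified for the month-12 survey, so missed 12-month patient-reported scores would probably be replaced by month-6 or older values

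*Protocol*

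**What the plan says.** **Survey schedule.** Under Follow-Up in the Protocol, "patients will receive this via secure email or text message link monthly for 6 months and then at 12 months". The secondary outcomes list gives the same time points for the AFEQT domains and the anticoagulation questions. No patient-reported measure is scheduled between months 6 and 12.

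**Chasing non-responders.** The next sentence reads: "During the first 6 months, if they do not respond within 24 hours, they will receive a reminder". A second reminder follows, and then: "Should there still be no response after an additional 48 hours, the RA will reach out to the patient via phone". No separate rule is given for month 12. The weekly automated message has a different purpose, "reminding patients to wear and sync their device", and the call attached to it is triggered by absent device data.

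**Use of the 12-month data.** Protocol item 12, Statistical Considerations: "In an additional secondary analysis, we will examine all of the outcomes at 12 months". SAP 1.6.1 repeats the primary analysis at 12 months and labels it exploratory.

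**Missing scores.** SAP 1.4: "If patient drop-out or loss to follow-up occurs, then we will carry forward the last patient-reported outcome measure response". SAP 1.6.1, in the paragraph on the 6-month analysis: "If patients are missing outcome data, we will use the last observation carried forward for the patient-reported outcomes". SAP 1.6.1, in the 12-month paragraph: "If a patient drops out, we will carry forward the most recent patient-reported outcome measure response".

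**Incentives.** Under Follow-Up and Payments for Participation, only control patients are paid for completing surveys. Apple Watch patients are told that keeping the watch carries an expectation of answering the monthly measures.

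**The concern.** The survey that follows the longest silence is the one with no stated follow-up. If it is missed, the analysis may not show it as missing. Because nothing is collected between months 6 and 12, the carried score is the month-6 score at best, yet it enters the table as a 12-month value. Change after month 6, in either direction, is diluted in proportion to the share carried forward.

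Because payment for surveys goes to one arm only, month-12 response could also differ by arm. Carrying scores forward would then turn a change common to both arms into an apparent difference between them.

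The Protocol's stated purpose is the effect over one year, so the 12-month patient-reported results will be read even though they are not primary.

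**Working it through.** **1. The plan's own sample size.** Inputs from SAP 1.4 and 1.1: difference 8.8, SD 18.5, 80% power, two-sided alpha 0.05, 8% non-completion at 6 months.

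- Per arm: 2 × (1.960 + 0.842)² × 18.5² / 8.8² = 69.4, so 70 per arm and 140 in total.
- Allowing for 8%: 140 / 0.92 = 152.2, so 153. The cruder 140 × 1.08 gives 152. Both are close to the planned 150.
- Check: 150 × 0.92 = 138 completers, 69 per arm, power 0.798.

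The figure of 150 reproduces. It rests on month 6, inside the reminder window, so this point does not disturb it.

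**2. How many scores could be carried forward.** The 8% is stated for month 6 only; using it at month 12 is an assumption, and so are 20% and 30%.

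- 150 × 0.08 = 12
- 150 × 0.20 = 30
- 150 × 0.30 = 45

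**3. Effect on the 12-month estimate.** Let *m* be the share carried forward from month 6, and *d6* and *d12* the true differences between arms at the two times. The analysed difference is

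(1 − *m*) × *d12* + *m* × *d6*.

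Assumptions: *m* equal in both arms; non-responders have the same mean differences as responders; 75 per arm; SD 18.5. The SAP gives that SD for the score, not for change from baseline. Power is taken as Φ(difference / (18.5 × √(2/75)) − 1.96), which is 0.83 for 8.8 with nothing carried forward.

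| Share carried | d6 = 0, d12 = 8.8: estimate (power) | d6 = 4.4, d12 = 8.8: estimate (power) | d6 = 8.8, d12 = 0: false difference |
|---|---|---|---|
| 8% | 8.10 (0.76) | 8.45 (0.80) | 0.70 |
| 20% | 7.04 (0.64) | 7.92 (0.75) | 1.76 |
| 30% | 6.16 (0.53) | 7.48 (0.70) | 2.64 |

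If *d6* equals *d12*, this mechanism produces no bias.

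**4. Unequal response.** Suppose there is no treatment effect, both arms shift by 5 points between months 6 and 12, and non-response is 10% in one arm and 30% in the other. The analysed difference is (0.90 − 0.70) × 5 = 1.0 point, in a direction that depends on the sign of the shift and on which arm responds less. These rates are assumed.

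**5. Does the carry-forward rule reach a patient who stays in the study but skips month 12?** The 12-month sentence and SAP 1.4 are triggered by drop-out or loss to follow-up. The broader trigger, any missing outcome data, stands in the 6-month paragraph, but the 12-month analysis is described as the same one. Carry-forward for a skipped survey is therefore the likely reading, not an explicit one.

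**The case against.** The strongest reply is that effort is placed where it counts. The primary outcome, the 8% allowance and the success criterion in SAP 1.3 all refer to 6 months, within the reminder window. The 12-month global score is declared exploratory, and the trial was not powered for it. That stands, and it limits the point to an improvement worth making.

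Several stronger readings are tempting, and the documents do not support them:

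- A reader might infer that all 12-month outcomes are exposed. Utilization, rhythm-control treatment and diagnostic testing come mainly from health records through Hugo, so a missed survey does not touch them. For anticoagulation, the SAP plans only to trend the answers and states no test between arms.
- A reader might infer that month-12 non-responders will not be contacted. The Protocol specifies no procedure but forbids none. Only the first of the three follow-up sentences carries the 6-month limit, although the other two read naturally as its continuation.
- A reader might infer that month 12 is sure to be the worst-answered survey, or that 20% to 30% will miss it. No response rate is given. Weekly device messages continue, so patients are not out of contact.
- A reader might infer a large distortion. Even where an 8.8-point difference has vanished by month 12, carrying forward 30% leaves a false difference of 2.64, below the plan's minimal important difference of 5.

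**Conclusion.** The point holds within limits. The current text specifies no chase for the month-12 AFEQT and anticoagulation survey. Any score carried to month 12 must be from month 6 or earlier. The effect falls on the exploratory 12-month global score and the 12-month patient-reported secondary outcomes: the AFEQT domains and, if the carry-forward rule is applied to it, anticoagulation persistence.

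The size cannot be fixed from the documents. Over the assumed 8% to 30% non-response, a difference that appeared or disappeared entirely after month 6 would be misstated by 0.70 to 2.64 points, and by less if the change were partial. This rests on equal non-response by arm and on carry-forward applying to every missing month-12 score. If the rule is confined to drop-out, fewer scores are replaced, but the missed surveys are still lost.

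**What to change.** In the Protocol's Follow-Up section, replace the opening limit to the first 6 months with wording that applies the two reminders and the RA call to every AFEQT and anticoagulation survey, including month 12. Name the 12-month close-out questionnaire in the same sentence: it is described separately, at the end of the Analytic Plan, so deleting the time limit alone would not reach it.

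Two small additions to the SAP would help. State whether carry-forward applies to a patient who remains in the study but skips month 12. Report, by arm, how many month-12 scores were observed and how many were carried forward. The reminders reduce the number of carried scores; they do not change the carry-forward rule.

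The cost is some extra automated messages and, at the assumed 8% to 30% non-response, at most 12 to 45 calls by staff who already make them. The sample size and the primary analysis do not change.

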### **Analytic Plan**

Baseline characteristics to be collected will be patient age, sex, location of primary care, location of primary cardiac care, and the comorbidities mentioned above. At baseline, patients will also be queried about their likelihood to use personal digital devices for health care purposes outside of this study, including if they have previously used a personal digital device and if they have previously used a personal digital device for cardiovascular monitoring.

Primary Outcome: Difference in the Atrial Fibrillation Effect on QualiTy-of-life (AFEQT) questionnaire global score at 6 months compared to baseline

### **Secondary Clinical Outcomes**

1. Change within individual domains of AFEQT questionnaire (symptoms, daily activities, treatment concern, and treatment satisfaction) monthly (at 1, 2, 3, 4, 5, and 6 months as well as at 12 months)
2. Additional clinical treatment for atrial fibrillation or flutter at 6 and 12 months: a composite outcome of rhythm control intervention, which is defined as at least one additional cardioversion, initiation of antiarrhythmic medical therapy, dose escalation of antiarrhythmic medication, change to another antiarrhythmic medication, or ablation for atrial fibrillation or flutter. The medication data will be obtained primarily from electronic health record data.
3. Acute care use at 6 and 12 months: emergency department visits, observation stays, all hospitalizations
4. Outpatient care use at 6 and 12 months: outpatient primary care visits, outpatient cardiology or cardiac electrophysiology visits, and scheduled telephone encounters.
5. Rhythm-related diagnostic testing at 6 and 12 months: total ECGs and total outpatient heart rhythm monitors
6. Anticoagulation persistence: through adopting the Brief Medication Questionnaire and asking patients if they have taken their anticoagulant, and for how many days in the past 1 week (monthly at 1, 2, 3, 4, 5, and 6 months as well as at 12 months)

For the primary outcome, we will calculate the difference in the AFEQT global questionnaire score at baseline and 6 months and perform a comparison between the patients randomized to the Apple Watch and patients randomized to Withings Move.

The secondary clinical utilization outcomes will be compared between the two groups. Data obtained through Hugo will be used to obtain most outcomes. Electronic health records will be used to review ECG tracings. We will also trend patients' monthly responses about anticoagulation adherence.

The secondary outcomes for accuracy of Apple Watch Software Features that will be compared are a comparison of the heart rhythm (identical to 12-lead ECG or different), rate (difference in beats per minute), and intervals: PR, QRS, and QT interval (difference in milliseconds) between what is assessed by the Apple Watch ECG feature and 12-lead ECGs during hospitalization or outpatient follow-up. This will be a blinded independent assessment of the Apple Watch ECG, and we will calculate both inter-observer reliability (among two reading cardiologists of Apple Watch ECGs), as well as intra-observer reliability.

As an exploratory outcome, we will aim to assess differences between SpO2 from the Apple Watch and medical grade readings.

The metrics we plan to collect are as follows:

A. Enrollment-related

- Number of people asked for study participation and number enrolled
  - Among patients who decline enrollment, if willing, the reason for declining

B. PROM-related (for all PROMs)

- Proportion of items completed
- Content of PROM responses

C. Personal Digital Device-related

- Number of patients who obtain Apple Watch ECGs over the study period, and the number of ECGs obtained
- Number of patients who receive an irregular rhythm notification during the study period, and the number of irregular rhythm notifications per patient
- Data obtained from Apple HealthKit and Withings Move

As each patient completes 12 months of follow-up, all patient data will be sent to the Mayo Clinic, where an analyst will clean and curate the data made available through the Hugo platform.

Finally, at the official end of the study (i.e. at 12 months post-procedure), study participants will receive a close-out questionnaire (see below) to assess occurrence of atrial fibrillation/atrial flutter, quality of life, anticoagulation medications, and device usage.

**4. Genetic Testing**      N/A

**5. Subject Population:** Provide a detailed description of the types of human subjects who will be recruited into this study.

We will recruit a total of 60 study participants undergoing cardioversion for atrial fibrillation or atrial flutter at Yale-New Haven Hospital. Yale-New Haven Hospital in New Haven, CT sees over 79,000 patients a year with

approximately 65,000 adult patients and there are approximately 1 to 3 cardioversions performed daily as well as more than 700 ablations annually.

6. **Subject classification:** Check off all classifications of subjects that will be specifically recruited for enrollment in the research project. Will subjects who may require additional safeguards or other considerations be enrolled in the study? If so, identify the population of subjects requiring special safeguards and provide a justification for their involvement.

Pregnant women or females of childbearing potential have the potential of being enrolled in this study but will not be specifically recruited for enrollment preferentially over other patients. We anticipate that this study presents minimal risk to pregnant women.

 Children	 Healthy	 Fetal material, placenta, or dead fetus
 Non-English Speaking	 Prisoners	 Economically disadvantaged persons
 Decisionally Impaired	 Employees	 Pregnant women and/or fetuses
 Yale Students	 Females of childbearing potential	

NOTE: Is this research proposal designed to enroll children who are wards of the state as potential subjects?  
Yes  No

7. **Inclusion/Exclusion Criteria:** What are the criteria used to determine subject inclusion or exclusion?  
Inclusion criteria:

- Age >22
- English-speaking
- Planned for direct current cardioversion for atrial fibrillation or atrial flutter, as noted by referring clinical staff or on chart review
- Post-procedure day 1 after catheter ablation for atrial fibrillation or atrial flutter
- Participant is willing and able to read and sign consent and participate in study
- Participant lives independently and does not require continuous care
- Participant has an email account (or is willing to create one)
- Participant has a compatible smartphone (iPhone 6s or later)
- Participant is willing to wear only the device they are randomized to receive for the study period for as many hours during the day as they are able, except for time spent charging the device or in environments that may be suboptimal for the device
- Participant is willing to use the Hugo mobile health platform and Apple Watch Series 6 or Withings Move
- Participant has cardiology care at YNHH, Duke Health, or Mayo Clinic and primary care in a health system with a patient portal

8. How will **eligibility** be determined, and by whom?

To be eligible, patients must meet the inclusion criteria listed above. A checklist will be used by the research associate (RA) to determine if the patient is eligible for this study.

For patients planned for cardioversion, once the scheduler or member of the clinical care team has introduced the study and if the patient has expressed interest in the study, the RA will review the patient's chart to confirm they have a history of atrial fibrillation or atrial flutter before contacting the patient. The RA will confirm that the patient meets all the eligibility requirements and discuss the specifics of the study described above. For inpatients, if a member of the clinical team identifies a patient that has been admitted to the hospital and will undergo DCCV in the next 24-48 hours that would qualify for this study, a clinician will inform the RA about the patient. The RA will then approach the patient and use a checklist to confirm the patient meets all of the eligibility criteria

For patients who are planned for catheter ablation for atrial fibrillation or atrial flutter, these patients will be informed by their physicians and screened for eligibility by research coordinators in advance of their procedure. Eligible patients will be identified on their first post-procedure day by research coordinators while the patient is recovering on the hospital ward, and usually planned for discharge, and eligibility will be confirmed prior to enrollment.

**9. Risks:** Describe the reasonably foreseeable risks, including risks to subject privacy, discomforts, or inconveniences associated with subjects participating in the research.

The risk to patient privacy is no different with this study than it is with any other study that securely collects and appropriately stores personally identifiable information or protected health information.

The Hugo platform, like many other personal health records, is not a covered entity; therefore, the HIPAA privacy rule does not apply to this platform. The Hugo Health platform does take all necessary precautions, including industry-standard encryption, to minimize privacy and security risks to personally identifiable information stored on behalf of study participants. Hugo Health makes publicly available its Security Statement (<https://hugo.health/security>), its Privacy Notice (<https://hugo.health/privacy-policy>), and Terms of Service (<http://hugo.health/terms-of-service>)

Participants will undergo the possible inconvenience of filling out electronic patient-reported outcome measure surveys, which should take no more than 10 minutes monthly for a total of 8 times, as well as a close-out questionnaire that should take no longer than 5 minutes. Participants will also experience the possible inconvenience of wearing an Apple Watch or Withings Move for extended periods of time and syncing these devices with the Hugo Health platform.

Although the Apple Watch ECG and irregular rhythm notification detection features have been cleared by the FDA as a de novo classification device, the FDA's approval letter noted multiple identified risks to health, which were:

Poor quality ECG signal resulting in failure to detect arrhythmia; misinterpretation and/or over-reliance on the device output, leading to: failure to seek treatment despite acute symptoms and/or discontinuing or modifying treatment for chronic heart conditions; false-negative resulting in failure to identify arrhythmia and delay of further evaluation or treatment; and false-positive resulting in additional unnecessary medical procedures. Further, we will clearly state to the patients that this study should in no way impact their regular care plans.

**10. Minimizing Risks:** Describe the manner in which the above-mentioned risks will be minimized.

All patient data will be collected, handled, and stored according to the most rigorous accepted standards. Staff involved in the study will be appropriately trained to maximize data security and technical systems will meet or exceed requirements imposed by HIPAA. Sensitive information will always be encrypted in transit and at rest.

11. **Data and Safety Monitoring Plan:** Include an appropriate Data and Safety Monitoring Plan (DSMP) based on the investigator's risk assessment stated below. (Note: the HIC will make the final determination of the risk to subjects.)

- a. What is the investigator's assessment of the overall risk level for subjects participating in this study? Minimal risk to patients
- b. If children are involved, what is the investigator's assessment of the overall risk level for the children participating in this study? No children will be involved in this study
- c. Include an appropriate Data and Safety Monitoring Plan. Examples of DSMPs are available here <http://your.yale.edu/policies-procedures/forms/420-fr-01-data-and-safety-monitoring-plans-templates> for
  - i. Minimal risk
  - ii. Greater than minimal

The principal investigators (PI) are responsible for monitoring the data, assuring protocol compliance, and conducting the safety reviews at the specified frequency regularly. During the review process the PIs will evaluate whether the study should continue unchanged, require modification/amendment, or close to enrollment.

The PIs or the Institutional Review Board (IRB) have the authority to stop or suspend the study or require modifications.

PROMs and syncable data received will not be reviewed by researchers, and this fact will be made clear to study participants at enrollment. Patients will be informed that symptoms reported in this study are not being monitored or evaluated in real-time and that any adverse or severe symptoms should be reported directly to their physician(s), or emergency room physicians as they would have in the normal course of their care.

The study coordinators will regularly monitor the status of the portal data (EHR/Apple Watch/Withings) coming into the Hugo platform using the Hugo study dashboard only available to research staff listed on the IRB. Within this dashboard, the research staff will be able to review the connection status of all portals connected to each patient's Hugo account. Should a connectivity issue be noticed by research staff, they will note the connection issue reported by the dashboard and determine if the issue is limited to one participant, or if multiple participants are experiencing the same problem. The research staff will then follow up directly with the Hugo support team.

Once the source of the issue is identified, research staff will follow up with the affected patients as needed to correct the issue in a timely fashion.

Research staff will also keep track of any technical issues reported by patients during their follow-up period. If the technical issues are not able to be resolved by the research staff, or if multiple patients report the same problem, the research staff will forward the issue to the Hugo Health support team to identify and correct the issue and in order to follow-up with those patients affected.

- d. For multi-site studies for which the Yale PI serves as the lead investigator:
  - i. How will adverse events and unanticipated problems involving risks to subjects or others be reported, reviewed and managed?
  - ii. What provisions are in place for management of interim results?
  - iii. What will the multi-site process be for protocol modifications?

12. **Statistical Considerations:** Describe the statistical analyses that support the study design.

All analyses will be intention-to-treat. For the primary outcome, we will calculate the difference in the AFEQT global questionnaire score at baseline and 6 months for patients randomized to the Apple Watch and patients randomized to the Withings Move arm.

The secondary clinical utilization outcomes will also be compared between the two groups using an intent-to-treat approach. Hugo will be the primary mechanism used to obtain clinical outcomes and clinical utilization, with comparisons between groups. We will also trend patients' monthly responses about anticoagulation adherence. In an additional secondary analysis, we will examine all of the outcomes at 12 months.

For the secondary outcomes for accuracy of Apple Watch Software Features that will be compared are a comparison of the heart rhythm (identical to 12-lead ECG or different), rate (difference in beats per minute), and PR, QRS, and QT intervals (difference in milliseconds) between what is assessed by the Apple Watch ECG feature and 12-lead ECGs during hospitalization or outpatient follow-up care. We will aim to compare the SpO2 readings taken by the Apple Watch at baseline to the measure taken by the standard, medical grade pulse oximeter

This sample size was calculated assuming 80% power to detect an effect size of 8.8 on the AFEQT questionnaire (slightly higher than the minimal clinically important difference of 5), with alpha 0.05.

